3.4 Finger tapping

3.5 Hand movements

3.6 Rapid alternating movements (pronation-supination of the hands)

These measures will be quantified using the Kinesia one accelerometer system (<http://glneurotech.com/kinesia/products/kinesia-one/>), which uses a propriety algorithm

to calculate a severity score on a 0-4 scale that has been shown to highly correlate with clinician ratings. The Kinesia one system has been used in multiple prior UF IRB approved studies and is FDA cleared to market and CE marked. The device is placed on the index finger during testing and senses movement.

Reaction time task: Subjects will look at a central fixation symbol on computer screen and press a computer keyboard/mouse button when the GO signal appears. The time between the onset of the fixation cross and the green GO signal will vary so that the onset of the GO signal will not be predictable. The time between appearance of the GO signal and recorded keyboard response will be recorded as reaction time.

Functional Dexterity Task (FDT): The FDT is a pegboard assessment of manual dexterity. It is a square pegboard with 16 holes and 16 pegs. Using a stopwatch, the examiner measures the time that it takes for the subject to turn over all the pegs on the board, as quickly as possible, using one hand at a time. A 5-s penalty is added every time the subject supinates or touches the board for assistance, while a 10-s penalty is added if the subject drops a peg. Two scores are obtained: the net time (in seconds) quantifies the speed of the hand dexterity; the total score (time plus penalties) quantifies the quality of the performance. The test ends when both hands have completed the task and the total score for each hand determines the functional level.

Timed-up-and-go (TUG) gait task: Subjects are asked to stand up from a chair, walk 3 meters to a horizontal line marked with red tape on the floor, turn around, walk back and sit down, at a comfortable pace. Two outcome assessments will be used during the TUG task. After obtaining video consent during the informed consent process, we will videotape the TUG test which will be scored by a blinded rater for number of freezing episodes and TUG completion time in seconds. The TUG task will be performed on the instrumented GAITRite mat (<https://www.gaitrite.com/>) which is located in the clinic and is routinely used for clinical care. The GAITRite mat measures and records spatiotemporal components of gait including stride length, regularity, cadence, left-sided step length,

right-sided step length, velocity, and an overall functional ambulation score. The GAITRite mat is FDA registered, CE Certified and ISO standard compliant.

Clinical Global Impression (CGI-I) Scale: The Clinical Global Impression-Improvement (CGI) scale was developed for use in NIMH-sponsored clinical trials.  It is a 7-point scale that requires the clinician to assess how much a specific symptom has improved or worsened relative to a baseline state prior to an intervention.

6.7b: Outcomes to be measured in subjects with ET:

FTM-TRS: Select measures from the Fahn-Tolosa-Marin Tremor Rating Scale (FTM-TRS).  The FTM-TRS is the most commonly used rating scale in clinical trials of essential tremor. It rates tremor on a scale of 0 (no tremor) to 4 (severe). Select measures of FTM-TRS to be tested are as follows:

- 5. right upper extremity tremor (rest, posture, action):
- 6. left upper extremity tremor (rest, posture, action):
- 10. Handwriting
- 22. Spiral drawing

Clinical Global Impression (CGI-I) Scale: as described above in PD section.

6.7c: Outcomes to be measured in subjects with dystonia:

TWSTRS: Select measures from the motor section of the Toronto Western Spasmodic Torticollis Rating Scale (TWSTRS).  The TWSTRS is the most commonly used rating scale to rate dystonia severity in patients with cervical dystonia. Ratings vary depending on the individual questions. Select measures of the TWSTRS section A to be tested are as follows:

- 1. Rotation
- 2. Laterocolis

3. Anterocollis/retrocollis
4. Lateral shift
5. Sagittal shift

Clinical Global Impression (CGI-I) Scale: as described above in PD section.

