## 6.5 Device Description and Previous Studies

The Vibrohealth system consists of 4 vibrating devices on bands and a magnetic contact charger (**Figure 1**). The devices are paired with a cell phone application (to be used solely by research investigators) that adjusts the parameters of vibratory stimulation during research visits (**Figure 2**).

The device consists of an actuator/sensor that, when placed against the surface of the skin, produces a vibrotactile sensation (vibration) through rapid lateral (side to side) motion. The intensity of the vibration produced by the Vibrohealth device is far less than that produced by commercially available massagers that provide vibratory stimulation for relaxation using similar technology. The sensor in the device is a tri-axial accelerometer and gyroscope that measures position using the same technology as smartphones.

A previous version of the Vibrohealth device was evaluated in 2017-2018 on 52 patients with PD and resting tremor at the Mount Sinai Hospital in New York City in a study funded by the device developer (Not Impossible). The Vibrohealth device was deemed

a nonsignificant risk device and was approved by full board IRB review (IRB #17-00555). There were no adverse events in any subjects receiving VTS. However, the stimulation setting intended to serve as a sham control setting (low amplitude continuous vibration) appeared to reduce resting tremor in approximately 60% of patients, suggesting that the vibration settings used in the protocol were inadequately investigated prior to study design. Though this study is being prepared for publication by the authors at Mount Sinai Hospital as a safety and feasibility study, the Parkinson

Foundation has decided to fund further pilot testing to ensure that any future clinical trials aimed at testing the efficacy of VTS are planned appropriately. We have tested the Vibrohealth device on 7 patients during our initial pilot testing since IRB approval without any adverse events.

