#### **6.6 Screening/Baseline Interview and Measures:**

Recruitment will be conducted at the UF Health Fixel Institute for Neurological Diseases via pre-review of outpatient appointments, review of the IRB approved movement disorders database, and during standard of care (SOC) visits. Clinic providers involved with the research study who provide clinical care/intervention for treatment may also discuss the protocol/research with their patient. If participants are identified through pre-review of outpatient records/lists/appointments, providers associated with clinical care for the subject will be notified of the subject's potential availability. No other information will be collected during the pre-screening process. The provider will then mention the study to the patient, if appropriate. When interested, subjects will either contact us about the study or the clinic providers will notify study coordinators of participant interest.

Study personnel will tell the potential participants about the study. The study personnel will consist of the investigators (UF faculty), staff study coordinators, and clinical movement disorders fellows. All study coordinators will be appropriately trained to meet HIPPA and IRB requirements. The pre-screening of records will only be carried out by study coordinators who already have approved EPIC medical record access.

Patients will also be identified using the Fixel Institute for Neurological Diseases patient database (Quantifying Deficits in Patients with Movement Disorders). Patients who have provided informed consent to have their medical information stored in the database and have indicated that they would like to be contacted about future research studies may be contacted (IRB201501166). Potential participants will be identified using database queries including diagnosis, age, location, most recent UPDRS, and most recent clinical visit. These identified potential participants will then be contacted by study coordinators to inform and invite them to participate in this research study.

Once a potential participant's interest in participating in the study is established, the study personnel will read from an approved telephone script to provide details about the study and the inclusion and exclusion criteria. If potential participants are still interested and are eligible to participate in the study, they will then be scheduled for an e-consenting appointment.

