## **7. Outcome and Statistical Approaches:**

For essential tremor and dystonia, the aims of this unblinded pilot study are to identify the optimal settings of VTS that are most promising to be tested in future clinical trials, statistical analysis will be limited to basic measures of central tendency. We will compare scores and values on the individual outcome measures listed above both on and off VTS, and within disease group means for each measure will be used to help guide the choice of settings to be tested in future studies. This pilot study will not be powered for between disease groups analysis or to test the efficacy of VTS for ET, or dystonia.

For Parkinson's disease, we expect to have data sufficient to justify exploratory statistical analysis. We have estimated that the number of patients included will allow for statistical analysis of patient's task performance before and during VTS. This was based on a medium effect size (Cohen's  $d = 0.50$ ) for the comparison of tremor power during VTS versus baseline. With an alpha of 0.05 and power of 0.80, the required sample size is 27 (based on a one-sided paired sample t-test). Thus, by recruiting 30 participants with PD, our sample size will give us sufficient statistical power to detect an effect with medium effect size. Statistical analysis will consist of a repeated measures ANOVA on the change in tasks performance scores relative to baseline. All post-hoc analyses will be corrected for multiple comparisons using Bonferroni correction.

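### Only the PD timed-up-and-go video has a blinded rater; the ET and dystonia ratings that guide the choice of settings have none, and two ET items could cheaply be scored blind

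*Combined protocol and SAP*

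**What the plan says.** Section 6.7a (PD) has the TUG test filmed and assigns the video to a masked assessor: "which will be scored by a blinded rater for number of freezing episodes and TUG completion time in seconds". No other assessment in the document is given a blinded rater.

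The CGI-I, also in section 6.7a, "requires the clinician to assess how much a specific symptom has improved or worsened relative to a baseline state" before the intervention. Nothing is said about whether that clinician knows the setting. Sections 6.7b (ET) and 6.7c (dystonia) carry the scale over unchanged: "Clinical Global Impression (CGI-I) Scale: as described above in PD section".

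The Functional Dexterity Task (FDT) in section 6.7a is timed by an examiner, who adds penalties for faults. No masking is stated.

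Section 7 is open about the two smaller groups: "For essential tremor and dystonia, the aims of this unblinded pilot study are to identify the optimal settings of VTS". Their analysis is descriptive, efficacy is not tested, and the within-disease means help select settings for later studies.

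On device control, section 6.5 states: "The devices are paired with a cell phone application (to be used solely by research investigators". Section 5 lists a sham setting that vibrates for 2 seconds at onset and then stops.

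**The concern.** A clinician who knows that stimulation is on, and which setting is running, may score the benefit that he or she expects. In PD the exposure is limited, because most outcomes are recorded by instrument. In ET and dystonia no instrument-recorded outcome is listed, so the choice of setting rests wholly on human ratings.

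The protocol's own rationale makes this matter. Section 3 says that few rigorously controlled trials exist. Section 6.5 reports that the intended sham in an earlier study appeared to reduce tremor in about 60% of patients. Section 11 tells participants that testing will be controlled and unbiased. Section 8 lists limitations but does not mention rater expectation. Calling a part of the study unblinded discloses the problem without reducing it.

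**Working it through.** **1. The plan's own figure.** Section 7 gives 27 patients for a one-sided paired t-test with d = 0.50, alpha 0.05 and power 0.80. With n − 1 degrees of freedom and non-centrality d × √n, n = 27 gives 0.50 × √27 = 2.60 and power 0.812. This is the smallest n that reaches 0.80, so the figure reproduces. The planned n = 30 gives 0.50 × √30 = 2.74 and power 0.848. The calculation concerns tremor power from an accelerometer, so masking of raters does not bear on it.

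**2. Who scores what (sections 6.7a to 6.7c).**

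| Group | Outcome | Scored by | Masking stated |
|---|---|---|---|
| PD | Tremor (Delsys), Kinesia items, reaction time, GAITRite | Instrument or algorithm | Not needed for scoring |
| PD | TUG video: freezing count, time | Human rater | Blinded |
| PD | FDT time and penalties | Examiner | None specified |
| PD | CGI-I | Clinician | None specified |
| ET | FTM-TRS items 5, 6, 10, 22; CGI-I | Clinical rating | Part declared unblinded |
| Dystonia | TWSTRS: five items; CGI-I | Clinical rating | Part declared unblinded |

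ET has 4 + 1 = 5 listed measures and dystonia has 5 + 1 = 6. All 11 are ratings, and none has a masking provision.

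**3. How bias reaches the decision.** If each on-stimulation rating is shifted by b through expectation, the mean on-minus-off difference is the true difference plus b at any sample size. With up to 5 patients per group (section 6.2) and no test planned, nothing in the analysis would reveal or absorb b. As an illustration, assume the rater moves a 0 to 4 item by one point in k of 5 patients. The mean then moves by k/5, from 1/5 = 0.2 (k = 1) to 5/5 = 1.0 (k = 5). The one-point shift and k are assumptions; the documents give neither.

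**4. What can be masked after the visit.** FTM-TRS items 10 (handwriting) and 22 (spiral) leave a paper record. Items 5 and 6, the TWSTRS items and CGI-I are judged live, and filming is described only for the TUG. Scoring from paper therefore reaches 2 of 5 ET measures and 0 of 6 dystonia measures.

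**5. Workload.** Assume one sheet per item per condition. Five patients × 2 items = 10 sheets per condition. Off plus one active setting gives 10 × 2 = 20 sheets, and each further setting adds 10. The number of settings tested in ET is not stated.

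**The case against.** The strongest reply is that section 7 declares the ET and dystonia part unblinded, limits it to description, disclaims any test of efficacy, and uses the means only to help guide later work. That stands: this is an openly chosen exploratory design, and nothing here contradicts itself. It does not answer the narrower point that two of the outcomes guiding the choice can be scored blind at almost no cost.

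A reader might infer more than the documents support:

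- **That all ratings could be masked without extra staff.** The list of personnel, "The study personnel will consist of the investigators (UF faculty), staff study coordinators, and clinical movement disorders fellows", stands in the section on recruitment. The documents do not say who attends testing, who operates the phone, who rates, or what the blinded rater's workload is.
- **That coded settings would mask on versus off.** Sham stops after 2 seconds, whereas active stimulation is continuous or intermittent, so the patient, and perhaps a rater in the room, may notice. PD measures are repeated before and during stimulation, and CGI-I is judged against a known baseline. Section 7 describes only on versus off for ET and dystonia and does not say how sham is used there.
- **That CGI-I in PD is declared unmasked.** The text is silent; masking is unspecified.
- **That a false-positive rate can be attached to the ratings.** This would need an assumed bias and a paired t-test. The plan uses that test to size the study on tremor power and does not specify it for CGI-I. The stated analysis is a repeated measures ANOVA on change in task performance.

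**Conclusion.** The point holds as a gap in masking and reporting, with one cheap improvement. The blinded TUG video is the only masked rating in the plan. CGI-I in all groups, FDT, FTM-TRS and TWSTRS have no masking specified, and all 11 listed ET and dystonia measures are clinical ratings whose means help guide the settings.

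The size of any bias cannot be taken from the documents; the 0.2 to 1.0 point range is illustrative. The consequence is confined to human-rated outcomes. The PD sample size and the instrument-recorded PD outcomes are untouched. Blind scoring of paper removes the rater's expectation from two ET items only. It does not remove the patient's expectation, and it leaves the live ratings as they are.

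**What to change.** 1. **Score the ET paper samples blind.** Label the handwriting (item 10) and spiral (item 22) sheets with a code that hides on/off status and setting, shuffle them, and have the rater already used for the TUG video score them after the visit. Cost: a code list and a small amount of that rater's time for up to 5 patients.
2. **State the roles.** Say who operates the phone application, who gives the live ratings, and whether the rater knows the setting. Where staff already present allow it, these should be different people. Cost: a sentence in the protocol; the split itself depends on staffing that the documents do not give.
3. **Report what stays unmasked.** Identify CGI-I, FDT, FTM-TRS items 5 and 6 and the TWSTRS items as unmasked wherever the rater knew the setting, interpret them accordingly when settings are chosen, and add rater expectation to the limitations in section 8. Cost: wording only.

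None of these changes alters the sample size, the stimulation settings or the visit procedures for participants.

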## **7. Outcome and Statistical Approaches:**

For essential tremor and dystonia, the aims of this unblinded pilot study are to identify the optimal settings of VTS that are most promising to be tested in future clinical trials, statistical analysis will be limited to basic measures of central tendency. We will compare scores and values on the individual outcome measures listed above both on and off VTS, and within disease group means for each measure will be used to help guide the choice of settings to be tested in future studies. This pilot study will not be powered for between disease groups analysis or to test the efficacy of VTS for ET, or dystonia.

For Parkinson's disease, we expect to have data sufficient to justify exploratory statistical analysis. We have estimated that the number of patients included will allow for statistical analysis of patient's task performance before and during VTS. This was based on a medium effect size (Cohen's  $d = 0.50$ ) for the comparison of tremor power during VTS versus baseline. With an alpha of 0.05 and power of 0.80, the required sample size is 27 (based on a one-sided paired sample t-test). Thus, by recruiting 30 participants with PD, our sample size will give us sufficient statistical power to detect an effect with medium effect size. Statistical analysis will consist of a repeated measures ANOVA on the change in tasks performance scores relative to baseline. All post-hoc analyses will be corrected for multiple comparisons using Bonferroni correction.

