## **5. Specific Aims:**

**Specific Aim. Evaluate the feasibility, reliability, and clinical effects of VTS on basic tasks of motor control and on the motor symptoms of patients with movement disorders.**

Hypothesis: VTS will produce beneficial effects on basic tasks of motor control and abnormal motor symptoms in patients with movement disorders. VTS Settings will include continuous stimulation between 60-120 Hz, intermittent stimulation at  $\frac{1}{2}$  baseline step frequency during walking, and sham stimulation (2 seconds of 30 Hz stimulation only at stimulation onset).

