## **6. Research Plan:**

### **6.1 Design Overview:**

This cross-sectional pilot study aims to identify the optimal device settings and preliminarily test the efficacy of the Not Impossible VibroHealth device in improving basic measure of motor control and symptoms in patients with PD and other movement disorders in the off-medication state. After informed consent, screening, and recruitment, the effects of VTS will be evaluated on basic tests of motor control and common movement disorders symptoms.

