#### Baseline testing:

MDS-UPDRS: Select measures from the motor section of the Movement Disorders Society Unified Parkinson's Disease Rating Scale (MDS-UPDRs). The MDS-UPDRS is a revision of the Unified Parkinson's Disease Rating Scale (UPDRS) originally developed in the 1980s. The scale is used in the clinic as well as in research to measure PD symptom severity. Individual measures are rated as 0 (normal) to 4 (severe).

Montreal Cognitive Assessment (MoCA): The MoCA is a cognitive screening test designed to assist Health Professionals in the detection of mild cognitive impairment and dementia. It will be used to exclude patients with cognitive impairment significant enough to confound the research variables of interest.

6.7a: Outcomes to be measured in subjects with PD:

Quantitative Tremor Assessment: An external accelerometer (Delsys Trigno; <https://delsys.com/trigno/>) will be adhered to the skin of the dorsum of the hand and will be used to quantify displacement of the hand due to tremor in the settings listed below. Delsys Trigno sensors have been used in multiple prior UF IRB approved studies and is FDA and CE registered with FCC ID, and is certified IEC601-1 (General Requirements for Medical Devices) and IEC601-1-2 (electromagnetic compatibility requirements for Medical Devices) with a UL recognized Internal Battery.

- 1. Sitting at rest
- 2. Sitting with both arms outstretched
- 3. Sitting at rest while performing a distracting cognitive task (reciting the months of the year backwards)
- 4. Transition from rest to posture (arms held directly in front of patient) for 10 seconds

Kinesia One accelerometer: The following select measures of MDS-UPDRS Part III: Motor Examination will be repeated before and during VTS:

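### For PD, the contrast that sizes the study is VTS against an earlier baseline, and Section 7 does not commit to the planned sham or to any control of setting order, so a VTS effect is not separated from session change

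*Combined protocol and SAP*

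**What the plan says.** - **Sizing.** Section 7 assumes a standardised effect of 0.50 "for the comparison of tremor power during VTS versus baseline" and concludes that "the required sample size is 27 (based on a one-sided paired sample t-test"). Thirty PD patients are planned.
- **Before and during.** Section 7 says that "the number of patients included will allow for statistical analysis of patient's task performance before and during VTS". Section 6.7a has the same order for the Kinesia items: "The following select measures of MDS-UPDRS Part III: Motor Examination will be repeated before and during VTS". Sections 6.7 and 7 also speak of testing on and off VTS, but no section places an off-VTS measurement after VTS.
- **Sham.** Section 5 includes among the VTS settings "sham stimulation (2 seconds of 30 Hz stimulation only at stimulation onset"). Section 7 does not mention sham.
- **Analysis.** "Statistical analysis will consist of a repeated measures ANOVA on the change in tasks performance scores relative to baseline", with Bonferroni correction of post-hoc tests. The factor, its levels and the post-hoc pairs are not named.
- **Order.** Section 6.7 fixes the order of outcomes within each disease group. No section gives the order of settings, a washout or a position term.
- **Session.** Testing is one visit of up to 4 hours, after medication has been withheld for 12 hours (Section 6.7). Section 10 allows rest breaks to limit fatigue.
- **Purpose.** Section 6.1 says the study "aims to identify the optimal device settings and preliminarily test the efficacy" of the device.

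**The concern.** Taking baseline first is not the fault. One setting is defined from "baseline step frequency during walking", the CGI-I is judged against a pre-intervention state, and the ANOVA uses change from baseline, so baseline has to come first. The difficulty is that VTS minus an always-earlier baseline estimates the VTS effect plus whatever else changed in between. Fatigue and time off medication could move tremor; practice matters more for the pegboard, reaction-time and walking tasks. The bias can go either way, and enrolling more patients does not shrink it.

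A sham measured in the same session would carry the same shared drift and remove it by subtraction, but Section 7 does not commit to that comparison. Even if it did, settings tested in an uncontrolled order could differ because of when they were tested. The study is meant to pick settings for later trials, so a setting could be carried forward because of its place in the session.

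**Working it through.** **1. The plan's own figure.** Inputs from Section 7: d = 0.50, one-sided alpha 0.05, power 0.80, paired t-test. Power = P(T > t(0.95, n−1)), where T is noncentral t with n−1 degrees of freedom and noncentrality d√n.
- n = 26: 0.798; n = 27: 0.812. The stated 27 is reproduced.
- n = 30: noncentrality 0.5 × √30 = 2.74; power 0.848.

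The arithmetic is right. The question is what the contrast measures.

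**2. Before/during test with no VTS effect.** Let δ be favourable drift between baseline and VTS, in SDs of the paired difference. The documents give no value, so δ is assumed. The noncentrality becomes δ√30.

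| δ | 0 | 0.05 | 0.1 | 0.2 | 0.3 |
|---|---|---|---|---|---|
| P(one-sided significant) | 0.050 | 0.084 | 0.134 | 0.283 | 0.484 |

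Adverse drift works the other way. With a true d of 0.5 and adverse drift of 0.2, the net effect is 0.5 − 0.2 = 0.3, and power falls from 0.848 to 0.484.

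**3. ANOVA on change, setting as factor.** Drift shared by all settings after baseline cancels; only drift between settings matters. Assume three settings, one common order for all 30 patients, linear drift g per block, and a between-setting difference with SD 1 (residual variance 0.5). The position means 0, g, 2g have squared deviations summing to 2g². The noncentrality is 30 × 2g² / 0.5 = 120g², on 2 and 58 degrees of freedom.

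| g | 0.05 | 0.1 | 0.2 | 0.3 |
|---|---|---|---|---|
| 120g² | 0.3 | 1.2 | 4.8 | 10.8 |
| P(falsely significant), common order | 0.072 | 0.145 | 0.466 | 0.825 |
| Six orders × five patients, no position term (simulated) | 0.05 | 0.05 | 0.04 | 0.03 |

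Simulation of the common order agrees (0.144 to 0.15, 0.46 to 0.47 and 0.83 for the last three columns). Rates below 5% arise because unmodelled drift inflates the error term; with a position term, active versus sham stays at about 5%.

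**4. Counterbalancing alone does not repair before/during.** With two counterbalanced settings, an active setting sits on average (1 + 2)/2 = 1.5 blocks after baseline. The one-sided test against baseline is then falsely significant 0.195, 0.481 and 0.775 of the time at g = 0.1, 0.2 and 0.3. The sham contrast is needed as well.

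**5. Power for active versus sham at n = 30.** d is the standardised active-minus-sham difference. The sham effects shown are assumptions.

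| Case | Net d | One-sided | Two-sided |
|---|---|---|---|
| Sham inert | 0.5 | 0.848 | 0.754 |
| Sham inert, Bonferroni over two active settings | 0.5 | 0.754 | 0.647 |
| Sham effect 0.1 | 0.4 | 0.690 | 0.563 |
| Sham effect 0.2 | 0.3 | 0.484 | 0.355 |

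For 80% two-sided power, net d of 0.5, 0.4 and 0.3 needs 34, 52 and 90 patients.

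**The case against.** The strongest reply is that sham is probably already in the analysis. A repeated measures ANOVA on change scores needs at least two within-patient levels, and the settings in Section 5, sham included, are the natural ones. Active versus sham would then be a post-hoc pair, and drift common to the settings would cancel. This stands: a reader might infer that the plan discards its sham, and the documents do not show that. What they show is that Section 7 leaves the factor and the pairs unnamed.

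Second, the 8 to 48% figures belong to the sample-size test, not to the stated ANOVA. That is correct, and the two are kept apart above. The before/during wording in Section 7 still leaves the simple contrast open.

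Third, drift may be small. The text is compatible with task-by-task testing, where baseline and VTS are minutes apart, and practice is an unlikely source of change in tremor at rest. This also stands; at 0.05 SD the rates are only about 8% and 7%. A reader might further infer that every patient gets the settings in one fixed order. No section says so, and the common-order figures depend on it.

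Fourth, this is an exploratory pilot, and Section 6.5 reports that an earlier, different sham appeared to reduce tremor in about 60% of patients, so sham may not be inert. That is a reason to report both contrasts and to state the loss of power. It is also a reason not to credit improvement from baseline to active VTS alone.

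**Conclusion.** The concern holds in a limited form, for PD only. The sizing contrast cannot separate VTS from session change, and the plan neither commits to the sham comparison that would remove shared drift nor says how setting order is controlled. The size of the resulting error is unknown. Over assumed drift of 0.05 to 0.3 SD, the false-positive rate runs from 8 to 48% for the before/during test, and from about 7 to 83% for the ANOVA if three settings ran in one common order. Those ranges rest on assumed drift size, linearity, block structure and number of settings.

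It does not follow that 27 is miscalculated, that the ANOVA is biased as planned, or that sham is excluded. No confounding claim is made for essential tremor or dystonia, where Section 7 limits the analysis to descriptive summaries. For an exploratory pilot this is a modest should-fix.

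**What to change.** **Section 6.7.** State that the off-VTS baseline is recorded first for PD, and that sham and the active settings applicable to each task then follow in an order taken from a pre-generated counterbalanced list. Balance the list over the number of settings a task has. If there were three, six orders with five patients each would cover 30; removing the walking-only setting from that list leaves the other two balanced 15/15 for seated tasks. State whether testing runs task by task or battery by battery.

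**Section 7.** Name setting, including sham, as the ANOVA factor, with position in the model so that dropouts do not upset the balance. Prespecify active versus sham in change from baseline as the contrast used to attribute an effect to VTS. Report before/during differences alongside it, labelled uncontrolled. Keep 30 patients, restate power for active versus sham, and say whether the test is one-sided or two-sided.

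**Cost.** Wording and one order list; no new equipment. The real price is lower stated power: a two-sided test at d = 0.5 falls short of the plan's 80%, and further if sham has an effect or Bonferroni is applied. For a pilot this is acceptable if stated. The design also assumes limited carryover between settings.
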